6.5 POOLING OF CENTRES

This section is not applicable, because the study was performed in only one centre.

6.6 HANDLING OF MISSING DATA AND OUTLIERS

Handling of missing data and outliers will be performed as described in the CTP, Section 7.4.

The only exception where imputation might be necessary for safety evaluation is AE dates. Missing or incomplete AE dates are imputed according to BI standards (see 001-MCG-156_RD-01 ([4](#))).

Missing data and outliers of PK data are handled according to BI standards (see 001-MCS-36-472_RD-01) ([5](#)).

If single cardiac cycles of an ECG (out of the generally four) are missing, the arithmetic mean for this single ECG will be computed with the reduced (1, 2 or 3) number of cardiac cycles.

If replicate ECG recordings are missing, the arithmetic means per time point will be computed with the reduced number (1 or 2) of recordings.

For the classification of the on-treatment QTc/QT intervals into “no new onset” / “new onset” categories, a missing value is obtained only in case that

- (i) all on-treatment values are missing and
- (ii) the baseline value is less than or equal to 500 msec, or missing.

If condition (i) is fulfilled but the baseline value is greater than 500 msec, this case will be categorized as ‘no new onset’. If baseline is missing and the maximum on treatment QTc interval is greater than 450 msec (or 500 msec for QT interval, respectively), this is classified as a ‘new onset’ in the respective category. If baseline is missing and the maximum QTc interval is less than or equal to 450 msec (or 500 msec for QT interval, respectively), this will be categorized as ‘no new onset’. If baseline is missing, a QTc/QT interval > 500 msec at any time on treatment will be a notable finding.

6.7 BASELINE, TIME WINDOWS AND CALCULATED VISITS

For vital signs or laboratory measurements, baseline is defined as the last measurement before drug administration (BI or Placebo).

Section 6.1 of the CTP: *Exact times of measurements outside the permitted time windows will be documented. The acceptable time windows for screening and end of trial examination are given in the CTP Flow Chart.*

Study measurements and assessments scheduled to occur ‘before’ trial medication administration on Day 1 of Visits 2 or 3 are to be performed and completed within a 2 h-period prior to the trial drug administration (including blank values for PK

Starting from 96 h post administration a deviation from the scheduled time for PK sampling ECG and blood sampling for ADA of \pm 70 min is acceptable. However, ECGs should always be time-matched with blood PK sampling.

The acceptable deviation from the scheduled time for vital signs and laboratory tests will be \pm 30 min for the first 72 h after trial drug administration. Starting from 96 h post

administration a deviation from the scheduled time for vital signs and laboratory tests of ± 70 min is acceptable.

Adherence to time windows will be checked via the consistency check listings at the RPM/DBLM.

There will be a centralised evaluation of the 12-lead ECG recordings at the time points and for the ECG recordings specified in the Table 6.7: 1 below:

Table 6.7: 1 Time schedule of 12-lead ECG recordings

Visit	Day	Planned time [hh:mm] (relative to drug administration)	Study phase	Central evaluation
1	-21 to -2		Screening	NA
2	-1	-24:00		NA
3	1	-1:00	On treatment	first of three replicate ECG
		-0:45		first of three replicate ECG
		-00:30		first of three replicate ECG
		06:00		first of three replicate ECG
		09:00		first of three replicate ECG
		12:00		first of three replicate ECG
	2	24:00		first of three replicate ECG
		28:00		first of three replicate ECG
		34:00		first of three replicate ECG
	3	48:00		first of three replicate ECG
		60:00		first of three replicate ECG
4		72:00		first of three replicate ECG
5		96:00		first of three replicate ECG
6		120:00		first of three replicate ECG
8		168:00		first of three replicate ECG
11		240:00		first of three replicate ECG
15		336:00		first of three replicate ECG
22		504:00		first of three replicate ECG
29		672:00		first of three replicate ECG
4	33 to 40		End of trial examination	NA

Triple ECGs (3 single ECGs of 10 sec duration each, recorded within 180 sec) will be recorded at all time points, except for Screening, planned time -24:00h and End-of-trial visit.

At these time-points single ECGs will be recorded. Three pre-dose triplicate ECGs within 60 minutes are to be recorded as baseline.

Section 6.1 of the CTP: *Only the first of the three replicate ECGs at a single time point or at baseline will be evaluated.*

The baseline value of an ECG variable is defined as the mean of the first single ECG measurement of each triple ECG prior to first drug administration.

7. PLANNED ANALYSIS

The placebo group in the safety evaluation will consist of all placebo treated subjects, regardless of the dose group in which they were treated.

Safety analysis (refer to [Section 7.8](#)) will be performed by and will be presented in Sections 15.1 to 15.4 of the CTR and in Appendix 16.2 and 16.1.13.1.

Descriptive data analysis of PK parameters and concentrations will be performed by the department Translational Medicine and Clinical Pharmacology (TMCP) at BI and will be presented in Section 15.6 and 15.7 of the CTR.

The format of the listings and tables will follow the standards defined in the BI corporate guideline “Reporting of Clinical Trials and Project Summaries” [001-MCG-159] ([6](#)) with the exception of those generated for PK-calculations.

The individual values of all subjects will be listed, sorted by treatment group, subject number, and visit.

The listings will be included in Appendix 16.2 of the CTR.

For end-of-text tables, the set of summary statistics for non-PK parameters is:

N	number non-missing observations
Mean	arithmetic mean
SD	standard deviation
Min	minimum
Median	median
Max	maximum

For analyte concentrations, the following descriptive statistics will additionally be calculated:

CV	arithmetic coefficient of variation
gMean	geometric mean
gCV	geometric coefficient of variation

For PK parameters, the following descriptive statistics will additionally be calculated:

CV	arithmetic coefficient of variation
gMean	geometric mean
gCV	geometric coefficient of variation
P10	10th percentile
Q1	1st quartile
Q3	3rd quartile
P90	90th percentile

The data format for descriptive statistics of concentrations will be identical with the data format of the respective concentrations. The descriptive statistics of PK parameters will be calculated using the individual values with the number of decimal places as provided by the evaluation program. Then the individual values as well as the descriptive statistics will be reported with three significant digits in the CTR.

Tabulations of frequencies for categorical data will include all possible categories and will display the number of observations in a category, as well as the percentage (%) for each treatment group. Percentages will be rounded to one decimal place and will be based on all subjects in the respective subject set whether they have non-missing values or not. The category 'missing' will be displayed only if there are actually missing values.

Units of variables should be given in the titles or column/row descriptors in square brackets (e.g. [mg]).

Exclusion of PK parameters

The analysis data set (ADS) ADPP contains column variables APEXC and APEXCO indicating inclusion/exclusion (APEXC) of a PK parameter and an analysis flag comment (APEXCO). All analyses based on the PKS will include parameters if they are not flagged for exclusion, that is APEXCO is equal to "Included".

Exclusion of PK concentrations

The ADS ADPC (PK concentrations per time-point or per time-interval) contains column variables ACEXC or ACEXCO indicating inclusion/exclusion (ACEXC) of a concentration and an analysis flag comment (ACEXCO). Exclusion of a concentration depends on the analysis flag comment ACEXCO. For example, if ACEXCO is set to 'ALL CALC', the value will be excluded for all types of analyses based on concentrations. If ACEXCO is set to 'DESC STATS' the value will be excluded from descriptive evaluations per planned time point/ time interval. If ACEXCO contains the addition 'TIME VIOLATION' or 'TIME DEVIATION' the value can be used for further analyses based on actual times. If ACEXCO is set to 'HALF LIFE' the value will be excluded from half-life calculation (and, as a consequence, any calculation that relies on λ_z) only; the value is included for all other analyses.

Further details are given in 001-MCS-36-472_RD-01 "Noncompartmental Pharmacokinetic / Pharmacodynamic Analyses of Clinical Studies" ([5](#)) and 001-MCS-36-472_RD-03 "Description of Analytical Transfer Files and PK/PD Data Files" ([11](#)).

7.1 DEMOGRAPHIC AND OTHER BASELINE CHARACTERISTICS

Only descriptive statistics are planned for this section of the report, based on the TS.

The data will be summarized by treatment group and in total.

7.2 CONCOMITANT DISEASES AND MEDICATION

Frequency tables are planned for this section of the report, based on the TS.

Concomitant diseases will be coded using the coding system of the Medical Dictionary for Drug Regulatory Activities (MedDRA). Medications will be coded using the latest version of the World Health Organization Drug Dictionary (WHO-DD). The coding version number will be displayed as a footnote in the respective output.

The diagnoses and medications will be listed. Subjects without any concomitant diagnoses or concomitant therapies should be marked with a “No” in the respective column.

The relevance of the concomitant therapies to the evaluation of PK will be decided no later than at the RPM/DBLM.

7.3 TREATMENT COMPLIANCE

Section 4.3 of the CTP: *Compliance will be assured by administration of all trial medication in the study centre under supervision of the investigating physician or a designee. The measured plasma concentrations of investigational and non-investigational medicinal products and urinary excretion of BI 473494 will provide additional confirmation of compliance.*

It is not intended to list the compliance separately. Any deviations from complete intake will be addressed in the RPM/DBLM (cf. TSAP [Section 6.2](#)) and described in the CTR.

7.4 PRIMARY ENDPOINTS

Refer to TSAP [Section 7.8](#) for a description of the analysis of safety and tolerability of BI 473494.

7.5 SECONDARY ENDPOINTS

7.5.1 Key secondary endpoints

This section is not applicable as no key secondary endpoint has been specified in the protocol.

7.5.2 Secondary endpoints

Descriptive statistics of plasma concentrations and PK endpoints will be done by the department TMCP at BI and will be presented in Section 15.6 of the CTR.

The analysis of PK parameters as well as the tables and graphs for the pharmacokinetic non-compartmental analyses will follow specific definitions of this TSAP or, otherwise, the BI standard procedure “Standards and processes for analyses performed within Clinical Pharmacokinetics/Pharmacodynamics” [001-MCS-36-472] ([7](#)).

7.7 EXTENT OF EXPOSURE

Descriptive statistics are planned for this section of the report based on the TS. The date and time of drug administration will be listed for each subject.

7.8 SAFETY ANALYSIS

All safety analyses will be performed on the TS.

If not stated otherwise, the safety results will be sorted by treatment group. The safety data for treated subjects who failed to complete the study (dropouts or withdrawals) will be reported as far as their data are available. All withdrawals will be documented and the reason for withdrawal recorded.

7.8.1 Adverse events

AEs will be coded with the most recent version of MedDRA.

The analyses of AEs will be descriptive in nature and will be based on BI standards as presented in the corporate guideline: “Analysis and Presentation of Adverse Event Data from Clinical Trials” [001-MCG-156] ([8](#)).

The standard AE analyses will be based on the number of subjects with AEs (and not on the number of AEs).

For analysis multiple AE occurrence data on the CRF will be collapsed into an AE provided that all of the following applies:

- All AE attributes are identical (LLT, intensity, action taken, therapy required, seriousness, reason for seriousness, relationship, outcome, AE of special interest)
- The occurrences were time-overlapping or time-adjacent (time-adjacency of two occurrences is given if the second occurrence started within one hour after end of the first occurrence).

For further details on summarization of AE data, please refer to [001-MCG-156] ([8,4](#)).

Section 5.2.2.1 of the CTP: *The following are considered as AESIs in this trial:*

- *Hepatic injury: A hepatic injury is defined by the following alterations of hepatic laboratory parameters:*
 - *an elevation of AST (aspartate aminotransferase) and/or ALT (alanine aminotransferase) ≥ 3 -fold ULN combined with an elevation of total bilirubin ≥ 2 -fold ULN measured in the same blood sample, and/or*

- aminotransferase (ALT, and/or AST) elevations ≥ 10 fold ULN

These lab findings constitute a hepatic injury alert and the patients showing these lab abnormalities need to be followed up according to the 'DILI checklist' provided in the ISF. In case of clinical symptoms of hepatic injury (icterus, unexplained encephalopathy, unexplained coagulopathy, right upper quadrant abdominal pain, etc.) without lab results (ALT, AST, total bilirubin) available, the Investigator should make sure these parameters are analysed, if necessary in an unscheduled blood test. Should the results meet the criteria of hepatic injury alert, the procedures described in the DILI checklist should be followed.

The analysis of adverse events will be based on the concept of treatment emergent adverse events.

Section 5.2.2.2 of the CTP: *The REP for BI 473494, when measurable drug levels or PD effects are still likely to be present after the last administration, is not known for this first-in-human trial. Therefore, all AEs reported until the end of trial examination (last per protocol contact) will be considered on treatment [...].*

For more details see the TSAP ADS plan.

According to ICH E3 (9), AEs classified as 'other significant' needs to be reported and will include those non-serious and non-significant adverse events with
(i) 'action taken = discontinuation' or 'action taken = reduced', or
(ii) marked haematological and other lab abnormalities or lead to significant concomitant therapy as identified by the Clinical Monitor/Investigator at the RPM at the latest.

An overall summary of AEs (including AESIs) will be presented.

The frequency of subjects with AEs will be summarised by treatment, primary system organ class (SOC) and preferred term (PT). Separate tables will be provided for subjects with other significant AEs according to ICH E3 (9), for subjects with serious AEs, for subjects with drug-related AEs, for subjects with drug related serious adverse events and for subjects with AESIs.

The SOC and PTs will be sorted by frequency (within SOC). The MedDRA version number will be displayed as a footnote in the respective output.

In addition, frequencies of subjects with non-serious AEs that had an incidence of $> 5\%$ for at least one treatment will be summarised by treatment, primary SOC and PT.

For disclosure of adverse events on EudraCT additional information not included in a standard AE analysis will be performed. The following three entries will be created:

- Adverse Events per arm for disclosure on EudraCT
- Non-serious Adverse Events for disclosure on EudraCT
- Serious Adverse Events for disclosure on EudraCT

7.8.2 Laboratory data

The analyses of laboratory data will be descriptive in nature and will be based on BI standards [001-MCG-157] ([10](#)).

Laboratory data will be analysed qualitatively via comparison of laboratory data to their reference ranges. Values outside the reference range as well as values defined as possible clinically significant will be flagged in the data listings.

It is the investigator's responsibility to decide whether a lab value is clinically significant abnormal or not (at the RPM/DBLM at the latest).

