7. STATISTICAL METHODS AND DETERMINATION OF SAMPLE SIZE

7.1 STATISTICAL DESIGN – MODEL

7.1.1 Objectives

The primary objective of this trial is to investigate the safety and tolerability of BI 473494 by using descriptive statistics for all endpoints comparing active dose groups to placebo. The primary endpoint is defined in [Section 5.2.1](#). Inferential statistics is not planned (as explained in [Section 7.2](#)).

The secondary objective is the exploration of the PK of BI 473494. Endpoints as specified in [Sections 5.5.1](#) and [5.7.1](#) will be analysed by descriptive statistics. Secondary endpoints as defined in [Section 5.5.1.1](#), as well as AUC_{0-168} and $AUC_{0-\infty}$, will be subjected to analysis of dose proportionality by use of the power model.

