7.3.3 Safety analyses

Safety will be assessed for the endpoints listed in [Section 5.2.1](#). All treated subjects (that is, all subjects who received at least one dose of study drug), will be included in the safety analysis. Safety analyses will be descriptive in nature and will be based on BI standards. No hypothesis testing is planned.

Treatments will be compared in a descriptive way. The placebo control group in the safety evaluation will consist of all placebo treated subjects, regardless of the dose group in which they were treated. The active treatment groups will be compared to the placebo group in a descriptive way. Tabulations of frequencies/proportions will be used for the evaluation of categorical (qualitative) data, and tabulations of descriptive statistics will be used to analyse continuous (quantitative) data.

The analyses will be done by 'treatment at onset'.

Measurements (such as ECG, vital signs, or laboratory parameters) or AEs will be assigned to treatments (see [Section 4.1](#)) based on the actual treatment at the planned time of the measurement or on the recorded time of AE onset (concept of treatment emergent AEs). Therefore, measurements planned or AEs recorded prior to first intake of trial medication will be assigned to 'screening', those between first trial medication intake until the end of trial visit will be assigned to the treatment period, and those after the end of trial examination will be assigned to 'post-study'. These assignments including the corresponding time intervals will be defined in detail in the TSAP.

Additionally, further treatment intervals (analysing treatments) may be defined in order to provide summary statistics for time intervals, such as combined treatments, on-treatment totals or periods without treatment effects (such as screening and post-study intervals).

Adverse events will be coded using the Medical Dictionary for Regulatory Activities (MedDRA). Frequency, severity and causal relationship of AEs will be tabulated by treatment, system organ class and preferred term. SAEs, AESIs (see [Section 5.2.2.1](#)) and other significant AEs (according to ICH E3) will be listed separately.

Laboratory data will be compared to their reference ranges. Values outside the reference range as well as values defined as clinically relevant will be highlighted in the listings. Additionally, differences from baseline will be evaluated.

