3. INTRODUCTION

As per ICH E9 (1), the purpose of this document is to provide a more technical and detailed elaboration of the principal features of the analysis described in the protocol, and to include detailed procedures for executing the statistical analysis of the primary and secondary variables and other data.

This trial statistical analysis plan (TSAP) assumes familiarity with the Clinical Trial Protocol (CTP), including Protocol Amendments. In particular, the TSAP is based on the planned analysis specification as written in CTP Section 7 “Statistical Methods and Determination of Sample Size”. Therefore, TSAP readers may consult the CTP for more background information on the study, e.g., on study objectives, study design and population, treatments, definition of measurements and variables, planning of sample size, randomisation.

Study data will be stored in a trial database within the Oracle ClinicalTM (O*C) system.

Pharmacokinetic (PK) parameters will be calculated using Phoenix WinNonlin™ software (version 6.3, Certara USA Inc., Princeton, NJ, USA).

The statistical analyses will be performed within the validated Clinical Analysis and Reporting Environment (CARE), including SAS™ (current Version 9.4, by SAS Institute Inc., Cary, NC, USA), and a number of SAS™-based tools (e.g., macros for the analyses of AE data or laboratory data; Report Appendix Generator system (RAGe) for compilation/formatting of the Clinical trial Report (CTR) appendices).

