4. CHANGES IN THE PLANNED ANALYSIS OF THE STUDY

All analyses described in the TSAP are outlined in the CTP. The following changes compared to the protocol will be made:

Dose escalation was stopped after the second dose group (75 µg BI 473494). Therefore, all analyses will be performed for the first and second dose group only.

- As there are only two dose groups available, no dose proportionality analysis will be done. Secondary endpoints (AUC_{0-tz} and C_{max} of BI 473494) will be analysed descriptively only.

- As there are only two dose groups available and only little exposure levels expected, no ECG exposure-response analyses will be done.

As an abbreviated CTR will be written, the change from baseline in body weight will be analysed descriptively only.

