7.8.3 Vital signs

Descriptive statistics over time including change from baseline will be performed for vital signs (blood pressure and pulse rate as well as body weight).

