7.8.4 ECG

12-lead ECG

Abnormal findings will be reported as baseline conditions (at screening) or as AEs (during the trial) if judged clinically relevant by the investigator.

All evaluations of ECG data will be based on the TS.

Listing of individual data

For all quantitative endpoints, listings of individual data will be shown in Appendix 16.2. For QTcB and RR only listings will be provided. Occurrences of notable findings will be flagged.

Comments regarding the ECGs will be listed.

Categorical endpoints

For the categorical endpoints, frequency tables will be provided.

For all subjects with any notable finding in ECG intervals, a separate listing will be created as end-of-text display (based on the same display template as in Appendix 16.2), and the corresponding time profiles will be shown.

Quantitative endpoints

Descriptive statistics (N, mean, SD, min, median, max) will be provided for the changes from baseline over time of QTcF, HR, QT, PR and QRS. The time profiles of mean and SD for the changes from baseline on treatment will be displayed graphically by treatment.

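### Does the SAP drop the laboratory differences from baseline that the protocol plans?

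*SAP*

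**What the plan says.** Protocol 7.3.3 has laboratory values compared with their reference ranges and then adds: "Additionally, differences from baseline will be evaluated". Protocol 7.1.1 sets the general aim of describing safety "by using descriptive statistics for all endpoints comparing active dose groups to placebo", and Protocol 5.2.1 lists safety laboratory tests among the further criteria of interest.

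SAP 7.8.2 says "Laboratory data will be analysed qualitatively via comparison of laboratory data to their reference ranges", with out-of-range and possibly clinically significant values flagged in the listings. It describes the analysis as descriptive and bases it on sponsor standard 001-MCG-157. It does not mention change from baseline.

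The neighbouring sections do. SAP 7.8.3 states "Descriptive statistics over time including change from baseline will be performed for vital signs", and SAP 7.8.4 says that descriptive statistics "will be provided for the changes from baseline over time of QTcF, HR, QT, PR and QRS". SAP 6.7 gives the baseline rule: "For vital signs or laboratory measurements, baseline is defined as the last measurement before drug administration (BI or Placebo". The visible items of SAP 4 cover the restriction to two dose groups, the dropped dose-proportionality and ECG exposure-response analyses, and body weight. None concerns laboratory data.

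**The concern.** The protocol plans two laboratory analyses, the SAP section names one, and no change is declared. The word chosen in SAP 7.8.2, qualitatively, points away from a numerical summary, and the contrast with the vital-signs and ECG sections makes the silence look deliberate.

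If the baseline differences really were dropped, a shift that stays inside the reference range would appear only in individual listings. Calcium and magnesium are the natural worry: Protocol 2.1 reports that both fell in monkeys at the low dose and uses that finding to set the starting dose. Both electrolytes are measured repeatedly (Protocol Table 5.2.3: 1), so the data for a change table will exist.

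SAP 4 also seems to offer a precedent, because it limits another change-from-baseline analysis on account of the shortened report: "As an abbreviated CTR will be written, the change from baseline in body weight will be analysed descriptively only".

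**Working it through.** No sample size, power or error rate is involved, so the check is mainly a comparison of the passages, with one short calculation on dose.

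**1. Planned against stated**

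| Item | Protocol 7.3.3 | SAP 7.8.2 | Visible SAP 4 |
|---|---|---|---|
| Reference-range comparison | planned | stated | no change declared |
| Differences from baseline | planned | not mentioned | no change declared |

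Two analyses are planned, one is stated and none is declared as changed. The factual core of the concern is correct.

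**2. What the rest of the SAP supplies**

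- SAP 3 gives the document's purpose as "to provide a more technical and detailed elaboration of the principal features of the analysis described in the protocol" and bases it on Protocol Section 7, which contains 7.3.3. A protocol analysis that SAP 4 does not alter therefore carries forward.
- SAP 6.7 defines a baseline for laboratory measurements by name. A comparison with reference ranges needs no baseline, so the definition has little use unless changes are calculated.
- SAP 6.1 plans tables of laboratory values by on-treatment phase, and that phase is kept separate for each treatment.
- SAP 7 fixes the statistics for end-of-text tables of non-PK parameters: N, mean, SD, minimum, median and maximum. Placebo subjects are pooled across dose groups for safety.
- SAP 7.8.2 defers to 001-MCG-157, which SAP 8 lists as the standard for handling, display and analysis of laboratory data.

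The baseline, the grouping, the statistics and the comparator are thus all specified. The one thing unstated is that the statistics are also applied to the change.

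**3. The body-weight item**

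SAP 4 limits change from baseline in body weight to descriptive analysis, and SAP 7.8.3 then includes body weight among the variables summarised with change from baseline. That summary was kept, so the item is no precedent for dropping a baseline comparison.

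**4. The calcium and magnesium signal**

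Protocol 2.1 gives the monkey dose as 20 µg/kg/week, the conversion factor as 3.1 and the reference body weight as 60 kg.

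- Human equivalent dose: 20 / 3.1 = 6.45 µg/kg; 6.45 × 60 = 387 µg.
- Ratio to the doses analysed: 387 / 35 = 11.1 and 387 / 75 = 5.2.

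The analysed single doses lie about 11 and 5 times below the scaled effect dose, which was given weekly. SAP 4 itself expects little exposure.

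**5. What would be lost in the worst case**

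The planned numbers are 6 subjects at 35 µg, 6 at 75 µg and 2 × 2 = 4 on pooled placebo; the SAP does not state the numbers treated. Individual values are listed (SAP 7), so changes can be calculated from the report. Clinically relevant laboratory changes are recorded as adverse events (Protocol 5.2.2.2) and so can count towards the primary endpoint.

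**The case for a change.** The strongest case for acting is that an analysis plan should not leave the reader to infer an analysis. The SAP promises detailed procedures, its two neighbouring sections name change from baseline, and this one does not. A programmer who took SAP 7.8.2 literally would deliver flags and listings only. The remedy would be one sentence, using data already collected. The dose argument also has a limit: the monkey effect was seen at the low dose, so the ratios of 11 and 5 do not show that nothing happens below 387 µg.

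Much of this stands. The wording is incomplete, and the reference to 001-MCG-157 cannot be checked here. It does not follow that the plan omits the analysis. Programmers do not work from one subsection, and the other SAP sections point the same way. Text may also be missing from the published SAP, whose contents list skips sections such as 6.4, 7.6 and 9, so silence is weak evidence of a dropped analysis.

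Precision does not decide the matter either. It would need a within-subject SD that the documents do not give, and Protocol 7.2 and 7.3.3 plan no safety tests.

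One neighbouring discrepancy is separate and should be reconciled by itself. Protocol 5.2.3 calls for laboratory samples after at least 10 h of fasting, while the Flow Chart places breakfast at 1:30 and lunch at 4:00, before the 6:00 sample. It affects how a 6 h change within one arm is read, and is a reason to read such a change beside the placebo column. It has no bearing on whether the change is summarised.

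**Conclusion.** The concern describes the text of SAP 7.8.2 correctly but does not call for a change to the plan. It is a gap in wording that analysts would fill sensibly: the protocol plans the differences, SAP 4 withdraws nothing on laboratory data, SAP 6.7 supplies the baseline, and SAP 6.1 and 7 supply the tables and statistics. Retention is the more plausible reading.

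The size is small. One descriptive safety summary is not named in its own subsection, for planned groups of 6, 6 and 4, with no effect on the primary endpoint or on any planned conclusion. This rests on two assumptions: that SAP 3 means what it says about carrying the protocol analysis forward, and that neither 001-MCG-157 nor any removed text withdraws the baseline comparison. A confirming sentence in SAP 7.8.2 would be good housekeeping and nothing more.
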